7.1.2 Leakage Scale

Needle leakage from the injections will be evaluated categorically according the droplet size at 6 different levels. Needle leakage is recorded using the 0 - 5 scale described in Figure 2. A binary leakage variable will be created with the equation below:

$$Y_{leak} = \begin{cases} \text{Yes, if recorded leak score} > 0 \\ \text{No, if recorded leak score} = 0 \end{cases} \quad (3)$$

7.1.3 Sub grouping Indicators

Indicator variables will be created to identify each of the following:

- Subjects with Asian ethnicity
- Subjects with a wash-in period

7.2 Analysis Method

This section provides a detailed description of the statistical analysis that will be performed in this study.

Unless otherwise stated, all the statistical tests are two-sided at a significance level of 5% and adjustment will be made for multiple comparisons when appropriate.

All the primary and secondary endpoints will also be analyzed as described below for the Asian sub-population.

7.2.1 Summary Statistics

Summary statistics (number of observations, mean, 95% CI for mean, median, standard deviation and range) for all quantitative responses will be presented in tables. Frequency tables with number of observations, percentage of total will be created for all discrete responses. All summary and descriptive statistics will be provided per pen needle group and overall.

Bar plots may be provided for some responses.

7.2.2 Statistical Methods

All Primary and Secondary analyses will be performed and presented per subgroup (Group 1 – Group 4) first (with no alpha adjustment). For each response, a statistical test will be performed to determine whether it is valid to combine the results from the four study groups into one overall result. If significant differences between the groups are identified, combined results will only include results from the groups exhibiting no significant difference. Groups that are significantly different (if any) will not be grouped into the overall result.

If a sufficient number of subjects having a two-weeks wash-in period, are enrolled in the study, a comparison of the responses may be performed. The comparison will be conducted between the subjects who did wash-in and those who did not wash-in for all groups pooled together. This assessment may be performed by including a “wash-in” effect into the analysis model. This is for information only.

A site effect will be investigated and if significant, comparisons between sites will be performed. This is for information only.

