2.0 OBJECTIVES

2.1 Primary Objectives

For all study groups combined, compare user preference for the BD Nucleus pen needle vs. current commercially available pen needles.

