13.3 Statistical Methods

All analyses will be performed and presented per subgroup (Group 1 – Group 4) first (with no alpha adjustment). For each response, a statistical test will be applied to determine whether it is valid to combine the results from the four study group into one overall result. If significant differences between the groups are identified, combined results will only include results from the groups exhibiting no significant difference; groups that are significantly different (if any) will not be grouped into the overall result.

If a sufficient number of subjects having a two-weeks wash-in period, are enrolled in the study, a comparison of the responses may be performed. The comparison will be conducted between the subjects who did wash-in and those who did not wash-in for all groups pooled together.

Descriptive statistics (number of observations, mean, standard deviation, minimum, maximum and 95% mean confidence interval) will be calculated and presented for all quantitative responses. Frequency tables with number of observations, percentage of total and 95% confidence interval (score method) for the percentage (as applicable) will be created for discrete responses.

Analysis for relative VAS: For each outcome measured on a relative VAS, a two-sided 95% confidence intervals will be calculated for the average rating. A modeling approach may be used to adjust for the visit effect (because of the often observed bias towards favoring the last PN used). Results will be tested for non-inferiority, followed by superiority:

If the lower bound of the CI is $> -10\text{mm}$, we can conclude in non-inferiority

If the lower bound of the CI is $> 0\text{mm}$, we can conclude in superiority

Analysis for needle breaking, needle bending, injection site bleeding, and bruising: A 95% confidence interval for the following difference in two independent proportions will be calculated using the score method:

$$\text{Proportion with BD Nucleus PN} - \text{Proportion with Current PN}$$

The upper bound of the confidence interval will be compared to the 4% NI criterion: non-inferiority will be concluded given the upper bound of the 95% score interval for the difference in proportions is $< 4\%$.

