3.2 Study Objectives

3.2.1 Primary Objectives

For all study groups combined, compare user preference for the BD Nucleus pen needle vs. the subjects' current commercially available pen needle.

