7.2.2.1 Analysis of Relative VAS Score

For each outcome measured on a relative VAS, a two-sided 95% confidence intervals will be calculated for the average rating. A modeling approach will be used to adjust for the order effect (because of the often observed bias towards favoring the last PN used). A linear model will be used to evaluate the pen needle group effect on the response to test whether the groups can be combined (a p-value < 0.05 for the pen needle group effect indicates non-poolability). In the model, the order of the pen needles used and the group to which the subject belongs based on their currently used or assigned pen needle will be used as covariates. LS means with CI will be obtained from the model and tested for non-inferiority, followed by superiority.

- If the lower bound of the CI is $> -10\text{mm}$, we can conclude in non-inferiority.
- If the lower bound of the CI is $> 0\text{mm}$, we can conclude in superiority.

Additional analysis: a *wash-in* indicator and an *Asian* indicator may be used to investigate these effects, as well as a site effect.

```
> #####
> ## Example R code to fit a linear model
> #####
> ##
> ## fitting the model
> model.fit=lm(vas_analysis ~ (NUCL_ORDER + PN_GROUP + ASIA)^2 + WASH_IN,
+             data=dataset, na.action=na.omit)
> #ANOVA table
> ## if p-value for PN_GROUP < 0.05, results not poolable across Groups
> anova(model.fit)
```

Analysis of Variance Table

Response: vas_analysis

	Df	Sum Sq	Mean Sq	F value	Pr(>F)
NUCL_ORDER	1	192	191.7	0.0928	0.7612
PN_GROUP	3	2757	919.0	0.4446	0.7215
ASIA	1	3215	3215.0	1.5554	0.2144
WASH_IN	1	751	750.8	0.3632	0.5477
NUCL_ORDER:PN_GROUP	3	3991	1330.3	0.6436	0.5882
NUCL_ORDER:ASIA	1	131	130.8	0.0633	0.8017
PN_GROUP:ASIA	3	308	102.6	0.0496	0.9853
Residuals	139	287317	2067.0		

```
> ##example contrast for the different pen needle groups
> ## given results not poolable,
> ## to identify which groups are not poolable
> ##
> model.fit=lm(vas_analysis ~ NUCL_ORDER + PN_GROUP,
+             data=dataset,
+             na.action=na.omit)
> ##
> library(multcomp)
> confint(glht(model.fit, linfct = mcp(PN_GROUP = "Tukey")))
```

Simultaneous Confidence Intervals

Multiple Comparisons of Means: Tukey Contrasts

```
Fit: lm(formula = vas_analysis ~ NUCL_ORDER + PN_GROUP, data = dataset,
na.action = na.omit)
```

Quantile = 2.5914

95% family-wise confidence level

Linear Hypotheses:

	Estimate	lwr	upr
Group 2 - Group 1 == 0	-9.0440	-33.6940	15.6060

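### If the groups differ on the preference VAS, the all-groups primary objective is decided on a reduced set of groups that is chosen after the outcome is seen and that the plan does not define

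*SAP*

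**What the plan says.** Protocol 2.1 sets the primary objective: "For all study groups combined, compare user preference for the BD Nucleus pen needle vs. current commercially available pen needles". SAP 3.2.1 opens the same way: "For all study groups combined, compare user preference for the BD Nucleus pen needle". Preference within each separate group is a secondary objective in both documents.

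The analysis rule is conditional. SAP 7.2.2.1 fits a linear model with order and group and states that "a p-value < 0.05 for the pen needle group effect indicates non-poolability". SAP 7.2.2 then applies: "If significant differences between the groups are identified, combined results will only include results from the groups exhibiting no significant difference", and "Groups that are significantly different (if any) will not be grouped into the overall result". Protocol 13.3 has the same rule: "groups that are significantly different (if any) will not be grouped into the overall result". SAP 11.2.1 adds that the all-subgroup result is shown only when the groups are poolable, and that otherwise the poolable groups alone are combined. Table 4, whose caption limits its overall row to poolable groups, carries the NI and superiority columns. Its example shows only the case in which all four groups pool.

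The only guidance on which groups to remove is a code comment in SAP 7.2.2.1, where Tukey contrasts are shown "to identify which groups are not poolable".

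Separately, SAP 7.2.1 promises descriptive figures: "All summary and descriptive statistics will be provided per pen needle group and overall".

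**The concern.** Two things go wrong when the group test is significant.

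First, the question changes. The objective names all four groups, but the formal overall conclusion covers only those that survive a test on the same outcome. No order-adjusted all-group estimate is then reported. The descriptive overall mean is not a substitute: it is not order-adjusted, although the SAP adjusts for order because users tend to favour the last needle used, and the NI rule is applied to the model-based LS means.

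Second, the surviving set is not defined. Six pairwise comparisons do not in general sort four groups into those that agree and those that do not. Nothing covers:

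- an intransitive pattern (A differs from C, B differs from neither);
- a significant group test with no significant pair;
- every group falling in some significant pair, so that none is left.

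The choice would be made with the outcome known, in an open-label study whose results are meant for marketing claims.

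**Working it through.** **1. The plan's own figures.** SD 35 mm, true mean +5 mm, margin -10 mm and two-sided 95% CI (Protocol 13.1, SAP 4) give noncentrality 15/(35/√n). Noncentral-t power is 90.4% at n = 60 and 80.3% at n = 45, matching the stated 90% and 80%.

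Table 4's combined row: the LS means in SAP 7.2.2.1 are 28.27822, 19.23421, 26.12959 and 18.67968.

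- Equal-weight mean = 92.3217/4 = 23.08.
- SE = √(5.634375² + 7.666839² + 8.028290² + 8.960491²)/4 = √235.27/4 = 3.83.
- With t(148) = 1.976, the CI is 15.50 to 30.66.

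Table 4 prints 23.1 (15.5, 30.7). Inverse-variance weights would give 24.27 (17.12, 31.41). The combined row is therefore the equal-weight, order-adjusted mean.

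**2. One data set, two answers.** Take 60 per group, SD 35 and residual df = 240 - 5 = 235. Suppose the observed group means are -15, -6, 0 and 5 (illustrative).

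- Group test: mean -4, squared deviations 121 + 4 + 16 + 81 = 222. F = (60 × 222/3)/35² = 4440/1225 = 3.62, p = 0.014. Not poolable.
- Tukey threshold: 2.588 × 35 × √(2/60) = 16.5 mm. Only -15 against 5 (20 mm) exceeds it.
- Lower limits use t = 1.970 and SE = 35/√(60k) for k groups:

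| Groups kept | Mean | Lower limit | NI |
|---|---|---|---|
| -15, -6, 0 | -7.00 | -12.14 | no |
| -6, 0, 5 | -0.33 | -5.47 | yes |
| -6, 0 (both members of the pair dropped) | -3.00 | -9.29 | yes |
| all four | -4.00 | -8.45 | yes |

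The first two sets are equally large and contain no significant pair. The plan does not choose between them, and they disagree on NI.

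**3. How often it matters.** The documents give no expected group differences, so the true means below are assumptions. I simulated 40,000 trials per row: SD 35; F test at 0.05; Tukey(-Kramer) pairs at 95% family-wise; t-based 95% CI on N - 5 df. NI rates are for (A) dropping every group in a significant pair, (B) keeping a largest set with no significant pair, ties broken at random, and (C) all four groups. My conventions: an empty set counts as no NI, and all four groups are kept if no pair is significant.

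| True means (n) | p < 0.05 | Groups removed | None left under A | NI: A / B / C |
|---|---|---|---|---|
| 5, 5, 5, 5 (60 each) | 5% | 4% | 0.2% | 99.8% / >99.9% / >99.9% |
| -2.5, 7.5, 7.5, 7.5 (60 each) | 32% | 30% | 4% | 96% / 99.9% / >99.9% |
| -10, 10, 10, 10 (60 each) | 91% | 89% | 49% | 50% / 99.6% / >99.9% |
| -10, 10, 10, 10 (60, 45, 45, 45; low group has 60) | 88% | 85% | 37% | 60% / 99% / >99.9% |
| 10, -10, 10, 10 (60, 45, 45, 45; low group has 45) | 81% | 79% | 34% | 64% / 99% / >99.9% |
| -25, -5, -5, -5 (60 each) | 91% | 89% | 50% | 0.6% / 44% / 2.4% |

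The 45-subject rows use the lower size that SAP 4 allows for Groups 2 to 4. Where groups are removed, the largest set is not unique in 57% of trials in the second row and 19% in the third. Superiority in the third row is 16% / 86% / 60%.

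**The case against.** **The rule is deliberate, and it does yield a decision.** Testing poolability before combining appears consistently in both documents, and every group gets its own order-adjusted conclusion, powered at 80 to 90%. A reader might infer that the plan gives no formal NI or superiority decision once the groups differ. The documents do not support that: Table 4's caption and its conclusion columns point to a formal overall row for the poolable groups. What stands is that this decision covers a narrower set than the objective names, and that the set is undefined.

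**The size depends on assumed heterogeneity and on readings I supplied.** That is true. With +5 mm in every group, readings A and B disagree on NI in only about 0.1 to 0.2% of trials. The low rates in the heterogeneous rows come from reading A, with an empty set counted as failure. Under B the NI rate is close to the all-group rate. The gap in the text does not depend on the simulation.

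**The last row might be read as type I error inflation.** It is not. The groups usually kept truly lie at -5 mm, inside the margin, so a statement limited to them can be correct. It answers a different question from the one about the four-group mean, which lies exactly at -10 mm. With all four means at -10 mm, NI rates are about 2.4% / 2.9% / 2.5%, near nominal.

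**A fixed four-group mean can hide a poor group.** It can: with true means -30, 10, 10, 10 it passes NI in 99% of trials. The current rule is not a dependable safeguard. Reading B removes the poor group and passes in almost 100%, while reading A almost always leaves no group. The per-group conclusions reveal the problem under either approach.

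**Conclusion.** The point holds. When the VAS group test has p < 0.05, the plan replaces the order-adjusted all-group result with a formal conclusion on a subset that is selected on the outcome and not defined. Beside it stand only the per-group conclusions, which serve a secondary objective, and an unadjusted descriptive overall mean.

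The consequence is small if the groups are alike. It is large if one group is well below the rest: with true means -10, 10, 10, 10 and 60 per group, the chance of concluding NI is 50% or 99.6% depending on how the rule is read. These rates rest on assumed group means, SD 35 mm and the conventions stated above. The finding in the text does not. It should be fixed, and before outcomes are seen.

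**What to change.** In Protocol 13.3 and SAP 7.2.2, 7.2.2.1 and 11.2.1, state that:

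- the primary NI and superiority conclusion, and the combined conclusion for the other relative-VAS endpoints, is always the order-adjusted, equal-weight LS mean over all four groups with its 95% CI, whatever the poolability p-value;
- the group test is reported as a heterogeneity check, beside the four per-group conclusions;
- any pooling of a subset is exploratory, names its groups, and follows a written step from Tukey pairs to the set, including when no pair is significant or no group is left.

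The diary proportions have their own poolability model and are outside this change.

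**Cost.** Protocol 13.3 contains the decision rule, so an amendment with IRB/EC approval is needed (Protocol 15.4), plus SAP wording. No new analysis is required, since Table 4's 23.1 (15.5, 30.7) is already this quantity. With a +5 mm average, the SE is 35 × √(4/60)/4 = 2.26 mm at 60 per group and 35 × √(1/60 + 3/45)/4 = 2.53 mm at 60, 45, 45, 45. NI power exceeds 99.9% in both cases.

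**Downsides.** The average can mask one poor group, so it must be read with the per-group conclusions. Equal weights reflect the enrolment quotas, not market use. Superiority may be concluded less often than on a favourable subset (60% against 86% for -10, 10, 10, 10).

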7.2.2.1 Analysis of Relative VAS Score

For each outcome measured on a relative VAS, a two-sided 95% confidence intervals will be calculated for the average rating. A modeling approach will be used to adjust for the order effect (because of the often observed bias towards favoring the last PN used). A linear model will be used to evaluate the pen needle group effect on the response to test whether the groups can be combined (a p-value < 0.05 for the pen needle group effect indicates non-poolability). In the model, the order of the pen needles used and the group to which the subject belongs based on their currently used or assigned pen needle will be used as covariates. LS means with CI will be obtained from the model and tested for non-inferiority, followed by superiority.

- If the lower bound of the CI is $> -10\text{mm}$, we can conclude in non-inferiority.
- If the lower bound of the CI is $> 0\text{mm}$, we can conclude in superiority.

Additional analysis: a *wash-in* indicator and an *Asian* indicator may be used to investigate these effects, as well as a site effect.

```
> #####
> ## Example R code to fit a linear model
> #####
> ##
> ## fitting the model
> model.fit=lm(vas_analysis ~ (NUCL_ORDER + PN_GROUP + ASIA)^2 + WASH_IN,
+             data=dataset, na.action=na.omit)
> #ANOVA table
> ## if p-value for PN_GROUP < 0.05, results not poolable across Groups
> anova(model.fit)
```

Analysis of Variance Table

Response: vas_analysis

	Df	Sum Sq	Mean Sq	F value	Pr(>F)
NUCL_ORDER	1	192	191.7	0.0928	0.7612
PN_GROUP	3	2757	919.0	0.4446	0.7215
ASIA	1	3215	3215.0	1.5554	0.2144
WASH_IN	1	751	750.8	0.3632	0.5477
NUCL_ORDER:PN_GROUP	3	3991	1330.3	0.6436	0.5882
NUCL_ORDER:ASIA	1	131	130.8	0.0633	0.8017
PN_GROUP:ASIA	3	308	102.6	0.0496	0.9853
Residuals	139	287317	2067.0		

```
> ##example contrast for the different pen needle groups
> ## given results not poolable,
> ## to identify which groups are not poolable
> ##
> model.fit=lm(vas_analysis ~ NUCL_ORDER + PN_GROUP,
+             data=dataset,
+             na.action=na.omit)
> ##
> library(multcomp)
> confint(glht(model.fit, linfct = mcp(PN_GROUP = "Tukey")))
```

Simultaneous Confidence Intervals

Multiple Comparisons of Means: Tukey Contrasts

```
Fit: lm(formula = vas_analysis ~ NUCL_ORDER + PN_GROUP, data = dataset,
na.action = na.omit)
```

Quantile = 2.5914

95% family-wise confidence level

Linear Hypotheses:

	Estimate	lwr	upr
Group 2 - Group 1 == 0	-9.0440	-33.6940	15.6060
Group 3 - Group 1 == 0	-2.1486	-27.5651	23.2678
Group 4 - Group 1 == 0	-9.5985	-37.0536	17.8566
Group 3 - Group 2 == 0	6.8954	-21.8716	35.6623
Group 4 - Group 2 == 0	-0.5545	-31.1299	30.0209
Group 4 - Group 3 == 0	-7.4499	-38.6268	23.7269

```
> ## Example for estimated pen needle subgroup means
> ##   if the lower CL is > -10, non-inferiority is satisfied
> ##   if the lower CL is > 0, superiority is satisfied
> library(lsmeans)
> lsmeans(model.fit, ~PN_GROUP)
```

PN_GROUP	lsmean	SE	df	lower.CL	upper.CL
Group 1	28.27822	5.634375	148	17.1440031	39.41243
Group 2	19.23421	7.666839	148	4.0835958	34.38482
Group 3	26.12959	8.028290	148	10.2647028	41.99447
Group 4	18.67968	8.960491	148	0.9726509	36.38671

Confidence level used: 0.95

7.2.2.2 Needle Bending, Injection site Bleeding and Bruising

For each pen needle group, a 95% confidence interval for the following difference in two independent proportions will be calculated using the score method.

$$\text{Proportion with BD Nucleus PN} - \text{Proportion with Current/Assigned PN}$$

Results will be tested for non-inferiority: If the upper bound of the CI is $< 4\%$, we can conclude in non-inferiority.

If results are poolable, results will also be presented for the groups combined. Poolability will be assessed through a mixed effects logistic regression model including a PN group by PN type interaction. If the interaction is significant, results are not poolable and only poolable groups will be presented combined.

```

> #####
> ## Example R code to test the difference in proportion of response
> #####
>
> ## Two-Sample difference in proportion test
>
> propdat <- data.frame(Break=c(45,56),NoBreak=c(780,810))
> row.names(propdat) <- c("BD Nucleus","Comparator")
> propdat$Total <- rowSums(propdat)
> propdat$Proportion <- propdat$Break/propdat$Total
> #
> library(PropCIs)
> ## 95% confidence interval
> #
> proptestci <- diffscoreci(x1=propdat["BD Nucleus","Break"],
+                           n1=propdat["BD Nucleus","Total"],
+                           x2=propdat["Comparator","Break"],
+                           n2=propdat["Comparator","Total"],
+                           conf.level=0.95)$conf.int
> #
> propest <- propdat["BD Nucleus","Proportion"] -
+   propdat["Comparator","Proportion"]
> #
> #if upper bound of CI < 0.04, NI satisfied
> data.frame(Estimate=propest,
+            CI = paste0("(",proptestci[1],", ", ",proptestci[2],")"))

```

Estimate	CI
1 -0.01011967	(-0.0330320064995986, 0.0127257649847972)

```

> #####
> ## Example R code for poolability testing
> #####
> library(lme4)
> ## mixed effects logistic regression model
> model = glmer(BLEEDING ~DEMO_PN_GROUP*RS_PN + (1 |SUBJ_ID),
+             data=diary, family=binomial,
+             control = glmerControl(optimizer = "bobyqa"))
> library(car)
> #if interaction p-value < 0.05, group results not poolable
> #

```

```

> Anova(model,type="III")

```

Analysis of Deviance Table (Type III Wald chisquare tests)

Response: BLEEDING

	Chisq	Df	Pr(>Chisq)
(Intercept)	186.7400	1	< 0.000000000000000022
DEMO_PN_GROUP	3.3702	3	0.337994
RS_PN	8.8563	1	0.002921
DEMO_PN_GROUP:RS_PN	14.6710	3	0.002120

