Analysis for needle leakage: Distribution of leakage scores will be provided and proportion of injections with recorded leakage score > 1 will be calculated per pen needles in each subgroup. Same analysis as for needle breaking, needle bending, injection site bleeding or bruising will be performed using proportion of injections with recorded leakage score > 1 as the response. Exploratory endpoints will be summarized with proportion of “Yes” answers and 95% score confidence interval.

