- If subject is currently on a 31G x 5mm or 32G x 5mm, they will randomized to either Group 3 (NovoTwist (32Gx5mm)) or Group 4 (MHC Easy Touch 5mm x 32G).
- If subject is currently on a 31G x 6mm or 32G x 6mm, they will randomized to either Group 2 (Novo Fine (32Gx6mm)) or Group 4 (Simple Diagnostics Comfort EZ 6mm x 32G).

Subjects who will remain on their current 32G pen needle will be required to visit the site a total of three times. Wash-in subjects will have an additional visit (Wash-in Visit) for a total of 4 visits (cf. Figure 1). Note that in the following document, “Current PN” and “Current/Assigned PN” are both used interchangeably to refer to the study arm where subjects did not use BD Nucleus PN.

The study will consist of two 15 day periods (± 3 days, no fewer than 13 days and no more than 17 days) in which the subject will use each pen needle (BD Nucleus pen needle or Commercially available 32G pen needle, order randomized) for injection.

Results will be compared to address the Primary, Secondary and Exploratory objectives. A final report will be issued summarizing all outcomes and conclusions.

Diagram 1 Subject Flow Chart

[figure not shown]

Figure 1: Subject Flow Chart

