3.4.2 Secondary Endpoints

- **Overall Comfort, Anxiety Associated with a Needle Stick Injury, Injection Pain, Ease of Use, Outer Cover Handling, Inner Shield Handling, Hub Comfort:** At the end of the last study period, each subject will be asked to evaluate his or her perception using a 150mm relative VAS scale. Average ratings will be used to assess non-inferiority and superiority.
- **Needle Bending or Injection Site Bleeding or Bruising:** After each injection, each subject will evaluate his/her perception of each by answering with a “Yes” or “No” response. The difference in percentage of “Yes” responses between the PNs will be used to assess non-inferiority.
- **Leakage:** After each injection leakage will be recorded using the scale below. Recorded leakage will be transformed to Yes/No scale and the difference in percentage of “Yes” responses between the PNs will be used to assess non-inferiority.

[figure not shown]

Figure 2: Subject Flow Chart

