3.5.2 Secondary Objectives

- Overall Comfort, Anxiety Associated with a Needle Stick Injury, Injection Pain, Ease of Use, Outer Cover Handling, Inner Shield Handling, Hub Comfort: Same as for primary objective
- Needle Breaking, Needle Bending, Injection Site Bleeding, Bruising and Leakage Score > 1: The difference in occurrence rate with BD Nucleus pen needle vs occurrence rate with Current pen needle will be compared to a 4% non-inferiority (NI) criteria.

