7.2.2.3 Analysis of Leakage

Distribution of leakage scores will be provided and proportion of injections with recorded leakage score >0 will be calculated per Pen Needles in each subgroup. Analysis as in Section 7.2.2.2 will be performed using the proportion of injections with recorded leakage score > 0 as response.

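### The 4% non-inferiority test on diary events treats every injection as independent and ignores that each subject uses both needles

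*SAP*

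**What the plan says.** SAP 7.2.2.2 states that for each pen needle group "a 95% confidence interval for the following difference in two independent proportions will be calculated using the score method". Non-inferiority is concluded if the upper limit is below 4%. Protocol 13.3 has the same rule and includes needle breaking: "A 95% confidence interval for the following difference in two independent proportions will be calculated using the score method".

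Leakage follows the same route with injections as the unit. SAP 7.2.2.3: "Analysis as in Section 7.2.2.2 will be performed using the proportion of injections with recorded leakage score > 0 as response". Protocol 13.3 says the analysis "will be performed using proportion of injections with recorded leakage score > 1 as the response". The two cut-offs differ, which is a separate matter; the interval problem is the same under either.

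The acceptance criteria in SAP 3.5.2 apply the 4% margin to "Needle Breaking, Needle Bending, Injection Site Bleeding, Bruising and Leakage Score > 1".

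On how the data arise, SAP 3.4.2 says "After each injection, each subject will evaluate his/her perception of each by answering with a" yes-or-no response. SAP 3.3 describes two 15-day periods "in which the subject will use each pen needle (BD Nucleus pen needle or Commercially available 32G pen needle, order randomized) for injection".

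The subject enters only one inferential step for these endpoints, the poolability model in SAP 7.2.2.2: "glmer(BLEEDING ~DEMO_PN_GROUP*RS_PN + (1 |SUBJ_ID". That model supplies an interaction p-value, not the interval that is compared with 4%. The table of subjects with at least one event (SAP 11.2.2, Table 6) is descriptive.

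**The concern.** The score interval for two independent proportions makes two assumptions that this design breaks. First, injections from one person are repeated measurements: someone who bleeds or bruises easily tends to do so again, so 34 injections from one subject carry less information than 34 injections from 34 subjects. Second, the same subjects supply both proportions, so the proportions are correlated.

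The two violations pull in opposite directions. Repeated injections make the true variance larger than assumed; sharing subjects makes it smaller. Which one dominates depends on the intraclass correlation (ICC) and on the correlation of a subject's event rate between periods. The plan states neither.

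The verdict depends on whether the upper limit lies below 4%, so a wrong width is a wrong error rate. SAP 3.1 says the outcomes are meant for marketing claims, so a false non-inferiority verdict on bleeding or leakage would have consequences even though these endpoints are secondary.

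**Working it through.** **1. Reproducing the plan's figures.** The SAP 7.2.2.2 code example compares 45/825 with 56/866. The difference is 0.0545 − 0.0647 = −0.0101, and a Miettinen-Nurminen score interval gives (−0.0330, 0.0127), which is the SAP's output. The same formula on the raw injection counts of Table 5 gives:

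| Group | Nucleus | Current | Difference (95% CI) |
|---|---|---|---|
| 1 | 65/2142 | 90/1998 | −1.5% (−2.7, −0.3) |
| 2 | 43/857 | 37/1020 | 1.4% (−0.4, 3.3) |
| 3 | 28/1023 | 31/906 | −0.7% (−2.3, 0.9) |
| 4 | 39/636 | 40/695 | 0.4% (−2.2, 3.0) |

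All four match Table 7. The planned n is therefore the number of injections, without adjustment.

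**2. Injections per subject and needle.** Dividing Table 5 denominators by Table 6 subject totals gives a range from 636/24 = 26.5 to 1998/54 = 37.0, and overall 9277/273 = 34.0.

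**3. Effect on the width.** Let m be injections per needle, ρ the ICC and c the correlation of a subject's two needle-specific rates. With equal event rates,

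true SE / assumed SE = √(1 + (m − 1)ρ − mρc) = √(1 + 33ρ − 34ρc) for m = 34.

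| ρ (assumed) | c = 1.0 | c = 0.8 | c = 0.5 |
|---|---|---|---|
| 0.02 | 0.99 | 1.06 | 1.15 |
| 0.06 | 0.97 | 1.16 | 1.40 |
| 0.10 | 0.95 | 1.26 | 1.61 |

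For example, at ρ = 0.06 and c = 0.5: √(1 + 1.98 − 1.02) = √1.96 = 1.40. For any ρ above zero the interval is too narrow once c falls below 33/34 = 0.97. At ρ = 0 the ratio is 1.

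**4. Effect on the error rate.** In simulation the true rates are 8% (Nucleus) and 4% (current), exactly at the margin, so the nominal false non-inferiority rate is 2.5%. There are 60 subjects, with beta-distributed subject rates and a Gaussian copula across periods. Two injection loads were used:

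- Load A: 1 to 5 injections a day for 15 days, with the illustrative Table 11 frequencies. The mean is (42 + 86 + 183 + 200 + 170)/230 = 2.96 a day, or 44.4 per period.
- Load B: a flat 34 per period.

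| ρ | Load | c = 1.0 | c = 0.8 | c = 0.5 |
|---|---|---|---|---|
| 0.02 | A | 3.1% | 3.8% | 6.1% |
| 0.02 | B | 2.5% | 3.6% | 4.6% |
| 0.06 | A | 3.6% | 7.4% | 11.3% |
| 0.06 | B | 2.9% | 5.6% | 9.0% |
| 0.10 | A | 3.6% | 11.7% | 16.3% |
| 0.10 | B | 3.6% | 7.6% | 12.7% |

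Here c is the latent correlation; the realised correlation of subject rates is a little lower (0.74–0.79 for 0.8, 0.42–0.49 for 0.5). Repeat runs agreed within about one percentage point. A subject-clustered paired interval gave 3.1–4.5% under load A and 2.7–4.0% under load B.

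- More subjects do not help. With 240 subjects, ρ = 0.06 and load A, the rates are 3.4%, 7.5% and 11.2% at c = 1.0, 0.8 and 0.5.
- With a rare comparator event (0.5% against 4.5%, ρ = 0.06) they are 11.4%, 12.1% and 14.6%. The comparator's between-subject variance is then too small for pairing to offset the clustering.

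**5. Illustration only.** SAP 11 says its tables come from test data that are not representative. In them, independence would imply that 61–86% of subjects have at least one bleed, while Table 6 shows 34–46%; the implied ICC is about 0.06 to 0.21. Recomputing Group 2 on that basis (ICC 0.170 and 0.152) moves its upper limit from 3.3% to about 4.9%, 4.0% and 3.2% at c = 0.5, 0.8 and 1.0. This shows how far a limit can move; it does not predict a verdict.

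**The case against.** The strongest counter-argument is that pairing cancels clustering. If a subject's tendency is almost the same under both needles, the planned interval is about right or slightly wide. This is correct as far as it goes. Even the sign at full sharing depends on the effect model: a constant additive shift gives 1.9–2.3% (slightly conservative), while the beta model above gives 2.5–3.6%. If events do not cluster at all, the test is also sound (2.2–2.5%). Neither case can be assumed, because nothing in the documents supports a cross-period correlation near 1 or an ICC near zero. The endpoints may also differ from one another.

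The size depends on the injection load. The figures based on Table 11 frequencies assume about 30% more injections than the 34 taken from Tables 5 and 6, and the flat-34 rates are lower. The inflation remains under both.

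The example data are not a basis for estimating the ICC, and that limit stands in full; the ICCs used for the error rates are an assumed range.

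The clustered interval does not restore exactly 2.5% either. That also stands, but its 2.7–4.5% in these scenarios is much closer than the planned method and does not depend on a lucky cancellation.

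Finally, the endpoints are secondary, and the SAP already declares the group analyses unadjusted for multiplicity. That limits the seriousness but does not justify a wrong standard error.

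**Conclusion.** The concern holds. The interval that decides the 4% test is wrong for data with repeated injections per subject in a crossover, and no other part of the plan corrects it. The accurate statement is that the error rate is not controlled, not that it is always inflated. For ICC 0.02 to 0.10 and cross-period correlation 0.5 to 0.8, false non-inferiority runs from 3.6% to 16.3% across the two injection loads, against 2.5% nominal. For a rare comparator event at ICC 0.06 it is 11% to 15%, even with full sharing. These sizes rest on assumed correlations and on the beta model. The point affects bending, bleeding, bruising and leakage, and needle breaking wherever the 4% criterion is applied to it. The primary preference analysis uses one score per subject and is untouched. This should be fixed, but it does not threaten the main conclusion of the trial.

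**What to change.** Keep the estimate (Nucleus minus current proportion of injections) and the 4% margin. Replace the interval in SAP 7.2.2.2, and by reference 7.2.2.3, with a 95% interval that takes the subject as the cluster and keeps both periods in the same cluster. Suitable choices are a GEE with identity link, independence working correlation and a small-sample-corrected robust standard error, or a bootstrap that resamples subjects. If within-subject differences are used instead, weight them by injections or declare a different estimand. Make the same change in Protocol 13.3.

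Prespecify a rule for few or no events, where robust and bootstrap intervals collapse. One option is a score interval with n divided by the design effect (robust variance over binomial variance), and a stated design effect if there are no events. At ICC 0.06 with 45 or 60 subjects this held 3.1–4.3%, including the rare-event case, where the plain robust interval gave 5.3–6.2%. The rule matters. With no events in either arm the score upper limit is about 3.84/(n + 3.84): 0.19% for n = 2040 injections (60 × 34), 0.56% for n = 680 (design effect 3) and 6.0% for n = 60 subjects. The documents give no basis for the design effect, so the sponsor must justify its choice before seeing the data.

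The cost is SAP and protocol wording and a few lines of R, with no new data. Intervals will usually be wider and some claims harder to make. With 60 subjects, a flat 34 injections, 4% event rates under both needles and ICC 0.10, power at cross-period correlation 0, 0.5 and 0.8 is 87%, 96% and 99% with a clustered interval, against 98%, 99.5% and 99.9% with the planned one.
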